
1 CLINICAL STUDY PROTOCOL

Study Short Name	Open-Label, Prospective, Multicenter Study to Assess efficacy			
Study Short Ivaine				
	and safety of Lactacol/Lactazak ®, a food supplement, in			
	intestinal colic and bloating			
Tested products	Lactacol/Lactazak ®			
	 The food supplement "Lactacol Fiale" (Lactacol), whose notification dated 20 November 2023 is annexed hereto, has the same formula as the food supplement "Lactazak" (PRG 570/2023). (Annex 1) Lactacol Fiale and Lactazak are the same food supplement with 			
	different trade names			
Study purpose	To assess efficacy and safety of Lactacol/Lactazak ®			
Market Status of the Tested Products	Notified to Health Ministry - General Directorate of Hygiene,			
	Food safety and nutrition protection - 20 November 2023			
Study Design:	Open-label, multicenter, prospective, non-comparative, non-			
	interventional study			
Protocol number	CBSPH_CBS27112023			
Protocol version	1.0			
Protocol date	Novemver 27 th , 2023			
Sponsor	Pharmunion LLC,			
	[name]			
Manufacturer	SALIX S.R.L.			
	[name]			
	[name]			
CRO	CEBIS International SRL			
	[name]			

Version 1.0/Date: November 27th, 2023

Open-Label, Prospective, Multicenter Study to Assess effiCacy and safEty of Lactacol/Lactazak ®, a food supplement in *intestinal colic and bloating*

Open-label, multicenter, prospective, non-comparative, non-interventional study

Protocol code: CBSPH CBS12122022

Version 1.0/Date: November 27th, 2023

SHORT name: PACE Study

CONFIDENTIALITY STATEMENT

The information contained in this document, especially unpublished data, is the property of CEBIS International (or under its control), and therefore provided to you in confidence as a potential participant or participant of this epidemiological study, potential investigator or consultant, for review by you, your staff and an applicable Independent Ethics Committee/Institutional Review Board. It is understood that this information will not be disclosed to others without written authorization from CEBIS except to the extent necessary to obtain informed consent from those persons to whom the tests may be applicable.

Version 1.0/Date: November 27th, 2023

1. Study Synopsis

1	Protocol	CBSPH_CBS27222023
1	identification:	Version 1.0/Date: November 27 th , 2023
	Protocol title:	Open-Label, Prospective, Multicenter Study to Assess efficacy and
2		safety of Lactacol/Lactazak ®, a food supplement, in intestinal colic and bloating
	Products involved:	
3	Troducts involved.	Lactacol/Lactazak ®
4	Study Design:	Open-label, multicenter, prospective, non-comparative, non-interventional
		study
	Dosage & administration:	. Product: LACTAZAK
	administration.	Route of administration: Oral route
		Single dose: 0.5 ml (700 FCC ALU).
		Maximum daily dose: 6 ml (8400 FCC ALU).
		Method of administration: Prior to use, twist the cap and shake
5		well, use a pipette to collect 0.5 ml of solution and give the baby
		before each breastfeeding or add to the milk formula for 14
		consecutive days.
		Lactacol/Lactazak ® is degraded, being exposure to high
		temperatures, so this enzyme should not be added to hot food or
		liquid. Store at room temperature (up to 25°C), away from heat
		sources and protected from light. Keep in the original packing. Keep
		out of the reach of children.

6	Number of subjects:	30		
7	Country	Bulgaria		
8	Investigators	GP, Pediatrics, Family Doctors		
9	No of centers to be involved	1-2		
		Primary Objectives		
		To assess the product efficiency by:		
		 reducing the baby crying due to colic during study period; reducing bloating 		
10		Secondary Objective		
10	Study objective	To assess effectiveness of the product administration by the responses at below questions during study period:		
		"How many hours in total does your child sleep per 24-h period?"		
		2. "How many hours in total do you (as caregiver) sleep per 24-h period?"		
		3. "How often does your child usually wake during the night?"		
		To assess safety of the product administration in terms of:		
		1. AE occurrence;		
		2. Withdrawals due to lack of tolerability		
	Study Endpoints	Primary endpoint		
		Efficacy will be evaluated by:		
11		reducing the number of babies crying episodes per day due to colic's during study period		
		 bloating reduction assessed though 3-point Likert scale Secondary endpoint 		
		Section of the point		

	T	T-00 : 1111 1 1 1 1 1 1 1 1 1 1 1 1 1 1 1			
		Effectiveness will be evaluated through the collected responses during			
		study period:			
		Change in mean number of hours of child sleep during 24 h, evaluated in a daily manner during study period through a journal			
		 Change in mean number of hours of caregiver sleep during 24 h, evaluated in a daily manner during study period through a journal 			
		3. Change in mean number of awakenings during night evaluated in a daily manner during study period through a journal			
		Safety will be assessed though:			
		1. Number of Adverse events;			
		2. Number of participants withdrawn due to lack of tolerability			
12	Sample size	30			
	Statistical Methods	Continuous data will be summarized in terms of the mean, standard			
		deviation (SD), median, minimum, maximum and number of			
		observations, unless otherwise stated. The minimum and maximum			
		will be reported to the same number of decimal places as the raw data			
		recorded in the database. The mean and median will be reported to one			
		more decimal place than the raw data recorded in the database. The SD will be reported to two more decimal places than the raw data recorded			
		_			
13		in the database. In general, the maximum number of decimal places reported shall be four for any summary statistic. Confidence intervals will be presented to one more decimal place than the raw data.			
		Categorical data will be summarized in terms of the number of patients providing data at the relevant time point (n), frequency counts and			
		percentages. Percentages will be presented to one decimal place. Percentages will not be presented for zero counts. Percentages will be			
		calculated using N (number per treatment group or overall) as the denominator.			
		denominator.			
14	Eligibility	Inclusion Criteria:			
		• pediatric population 0-4 months;			

		• Established diagnosis: FGIDs (intestinal colic and bloating).	
		Signed Informed Consent for data collecting;	
		Exclusion Criteria:	
		Unwillingness to provide signed Informed Consent for data collecting;	
		 Patients participating in other trials 	
		Allergy to any of the product ingredients	
	Visits:	3 visits:	
15		 Visit 1 - Screening and enrollment visit; Visit 2 - Day 14 from Therapy initiation; Visit 3 - Phone Follow-up 	
16	Study procedure	This non-interventional study will be conducted in Bulgaria in routine clinical practice by GP, pediatricians, family doctors. Data will be collected prospectively. Lactacol/Lactazak® will be administered in accordance with approved leaflet. Patient demographic data would be collected during screening visit where available (e.g., age, gender, geographic location, Apgar score, type of birth method) All the assessments for primary and secondary objectives will be performed at baseline and periodically according to the national	
17	Concomitant	standards, routine clinical practice, and this study protocol. All concomitant medications taken or administered in the 6 weeks	
1 /	medications	before screening and during the study will be documented in the CRF.	
		Adverse events will be monitored and reported accordingly.	

Version 1.0/Date: November 27th, 2023

2 LIST OF ABBREVIATIONS

AE	:	Adverse Event
BMI	:	Body Mass Index
CRF	:	Case Report Form
GCP	:	Good Clinical Practice
GI	:	Gastro intestinal
ICF	:	Informed Consent Form
ICH	:	International Conference on Harmonization
IMP	:	Investigational Medicinal Product
No	:	Number

Version 1.0/Date: November 27th, 2023

5 PROJECT TITLE

Open-Label, Prospective, Multicenter Study to Assess efficacy and safety of Lactacol/Lactazak ®, a food supplement, in intestinal colic and bloating

6 PROTOCOL CODE AND VERSION:

Protocol code:	CBSPH_CBS27112023
Version & Date	Version 1.0/Date: November 27 th , 2023

7 OBJECTIVES

Primary objective:

To assess the product efficiency by:

- reducing the baby crying due to colic during study period;
- reducing bloating

Secondary objective:

To assess effectiveness of the product administration by the responses at below questions during study period:

- "How many hours in total does your child sleep per 24-h period?"
- "How many hours in total do you (as caregiver) sleep per 24-h period?"
- "How often does your child usually wake during the night?"

To assess safety of the product administration in terms of:

- AE occurrence;
- Withdrawals due to lack of tolerability

Version 1.0/Date: November 27th, 2023

8 BACKGROUND

The most prominent feature of Infant Colics is prolonged crying. Additional characteristics, including clenching of the fists and flexion of the hips, have led to the suggestion that these behaviors are related to abdominal discomfort; thus, the term "colic, "derived from kolikos, the Greek term for colon. Infant colic is challenging for new parents and is a reason for 10% to 20% of paediatrician visits during the early weeks of an infant's life. Colic is estimated at affecting 5% to 40% of infants worldwide. The condition typically presents in the second or third week of life, peaks around 6 weeks, and resolves by the age of 12 weeks in 60% of infants and by 16 weeks of age in 90%. Inconsolable crying, irritability, and screaming without an obvious cause characterize colic; during these episodes of fussiness, which occur more frequently in the evenings, the affected infant classically appears red-faced, draws up the legs and tenses up the abdomen. The traditional methods of soothing the infant often fail to relieve the infant's distress. First described in 1954, the original "Wessel's Rule of 3s" diagnostic criteria (symptoms lasting for 3 hours per day, 3 or more days per week, for 3 or more weeks, starting around 3 weeks of age), has undergone a transition in recent years. The Rome IV criteria describe colic in infants from birth to 5 months of age to make the definition of infantile colic more consistent for research purposes. The criteria are as follows:

- An infant who is <5 months of age when the symptoms start and stop
- Recurrent and prolonged periods of infant crying, fussing, or irritability reported by caregivers that occur without obvious cause and cannot be presented or resolved by caregivers
- No evidence of infant failure to thrive, fever, or illness

While benign and self-limiting, the condition is frustrating for parents and has been linked to maternal postpartum depression and shaken baby syndrome. Since treatments for colic are controversial and inconsistent, the role of the physician as a counsellor and educator to parents is critical. The several factors involved in the etiopathogenesis (food intolerance or allergy to cow's

Version 1.0/Date: November 27th, 2023

milk protein, intolerance to lactose, intestinal hyperperistalsis, neuro-hormonal immaturity, maternal anxiety and familial stress), make the management of infants with colics difficult.

Studies have shown up to 40% of babies medically diagnosed with colic actually suffer from transient lactase intolerance, hence the common term "colic associated with lactose intolerance".

Many of these babies can be helped by pre-treating baby's feeds with lactase enzymes.

LACTOSE INTOLERANCE is typically a temporary condition for babies and small children.

- Often young babies don't produce enough of the enzyme (lactase) because of functional "immaturity of" intestinal enzyme systems
- Lactose overload breastfeed babies consuming large amounts of breastmilk (usually when their mothers have an oversupply)
- Gut damages: gastroenteritis, food intolerance or allergy, parasitic infection, coeliac disease, bowel surgery
- Rare genetic condition: primary (or true) lactose intolerance Infant colic is a characteristic group of behaviors seen in young infants.

A commonly used set of diagnostic criteria was proposed by Morris Wessel and colleagues,1 based on observations of 98 infants in the newborn nursery at Yale, 25 of whom had inconsolable crying. These criteria are summarized by the frequently quoted "rule of 3s": crying by an otherwise healthy infant that lasts more than 3 hours per day on more than 3 days a week for more than 3 weeks

Pediatricians often use the "Rule of Three" to diagnose colic. Child who cried:

- for more than 3 hours a day
- for more than 3 days a week
- for over 3 weeks

When using the enzyme lactase before each feeding (breast milk and/or a mixture) baby crying because of colic was reduced by half during clinical study.

Version 1.0/Date: November 27th, 2023

The study Sponsor introduce Lactacol/Lactazak®, which can be used as dietary supplement to a healthy diet and as a source of lactase enzyme. Lactacol/Lactazak® characteristics are:

- Contains highly active lactase enzyme of plant origin.
- Resistant to acidic gastric medium.
- Maintains its activity in the conditions of high pH variations.

Lactacol/Lactazak promotes lactose hydrolysis **and it** should be used during each feeding during the first 3-4 months of life. After this period, lactase enzyme is usually produced by the body in sufficient quantities. Lactacol/Lactazak should be gradually withdrawn from feedings.

9 STUDY DESIGN

Open-Label, Prospective, Multicenter Study

10 STUDY TYPE

Observational study

11 FACILITIES

[figure not shown]
Selected sites in Bulgaria

12 STUDY INVESTIGATORS

GP, pediatricians, family doctors at individual cabinets will recruit the subjects. Adequate number of subjects will be selected and will undergo a standardized screening.

13 STUDY POPULATION

The investigators will enroll in this study 30 subjects accordingly to the inclusion and exclusion criteria.

STUDY TREATMENT

Paediatric patients will be enrolled after diagnosis with intestinal colic and bloating. They will be

treated with Lactacol/Lactazak ® as presented below:

Product: LACTAZAK, Route of administration: Oral route, Single dose: 0.5 ml (700 FCC

ALU). Maximum daily dose: 6 ml (8400 FCC ALU).

Method of administration: Prior to use, twist the cap and shake well, use a pipette to collect 0.5

ml of solution and give the baby before each breastfeeding or add to the milk formula for 14

consecutive days.

LACTAZAK is degraded, being exposure to high temperatures, so this enzyme should not be

added to hot food or liquid. Store at room temperature (up to 25°C), away from heat sources and

protected from light. Keep in the original packing. Keep out of the reach of children.

15 STUDY PROCEDURES

This non-interventional study will be conducted by family doctors/Peditrcians in Bulgaria

in routine clinical practice. Data will be collected prospectively. Lactacol/Lactazak® will be

administered in accordance with approved leaflet. Patient demographic data would be collected

during screening visit where available (e.g., age, gender, geographic location, Apgar score, type

of birth method)

All the assessments for primary and secondary objectives will be performed at baseline

and periodically according to the national standards, routine clinical practice and this study

protocol. Medical histories and demographic data (including subject's initials, date of birth) and

medication used will be recorded into patient file.

Subjects will attend 3 visits during the study:

Visit 1 (Baseline):

Version 1.0/Date: November 27th, 2023

- Concomitant medication
- Patient evaluation of eligibility criteria
- Patient informed consent
- Evaluation of baby crying episodes
- Bloating evaluation
- Child sleep evaluation
- Caregiver sleep evaluation
- Patient Medical History
- Physical examination (weight, height, abdominal girth blood pressure, pulse, temperature, respiration, BMI)
- Treatment Allocation

Visit 2 – Day 14

- Adverse events
- Concomitant medication
- Evaluation of baby crying episodes
- Bloating evaluation
- Child sleep evaluation
- Caregiver sleep evaluation
- Physical examination (weight, height, abdominal girth blood pressure, pulse, temperature, respiration, BMI)
- Recurrence evaluation*
- Treatment adherence **

Visit 3 – Day 28 (Phone Follow-up)

- Adverse events
- Concomitant medication
- Evaluation of baby crying episodes
- Bloating evaluation
- Child sleep evaluation
- Caregiver sleep evaluation

Version 1.0/Date: November 27th, 2023

Study Flowchart

Study Flowchart	Visit 1 (Baseline)	Visit 2	Visit 3 Phone Follow-up
	Day 0	Day 15 +/- 2 days	Day 28 +/- 5 days
Patient informed consent	X		
Physical examination	X	X	
Patient evaluation of eligibility criteria	X		
Patient Medical History	X		
Concomitant medication	X	X	X
Evaluation of baby crying episodes	X	X	X
Bloating evaluation	X	X	
Child sleep evaluation	X	X	X
Caregiver sleep evaluation	X	X	X
Product Allocation	X		
Product adherence		X	
Product administration	X	X	
End of product administration		X	
Adverse events		X	X
Investigator Final evaluation on patient status			X

16 OUTCOMES

Primary endpoint

Efficacy will be evaluated by:

- reducing the number of babies crying episodes per day due to colic's during study period
- bloating reduction assessed though 3-point Likert scale

Pharm

Protocol code: CBSPH_CBS27112023

Version 1.0/Date: November 27th, 2023

Secondary endpoint

Effectiveness will be evaluated through the collected responses during study period:

- 4. Change in mean number of hours of child sleep during 24 h, evaluated in a daily manner during study period through a journal
- 5. Change in mean number of hours of caregiver sleep during 24 h, evaluated in a daily manner during study period through a journal
- 6. Change in mean number of awakenings during night evaluated in a daily manner during study period through a journal

Safety will be assessed though:

- 3. Number of Adverse events;
- 4. Number of participants withdrawn due to lack of tolerability

17 INVESTIGATED MEDICAL PRODUCT

17.1 Lactacol/Lactazak

Lactacol/Lactazak® promotes lactose hydrolysis. It helps lactose digestion by reducing fermentation and gas production. Lactacol/Lactazak® should be used during each feeding during the first 3-4 months of life. After this period, lactase enzyme is usually produced by the body in sufficient quantities, and Lactacol/Lactazak® should be gradually withdrawn from feedings.

17.2 Composition of Lactacol/Lactazak

Use as a dietary supplement to a healthy diet and as an additional source of lactase enzyme. **INGREDIENTS**: Sunflower oil; Lactase (Beta-galactosidase); Maltodextrin; Anti-caking agent: mono-and diglycerides of fatty acids (or E 471); Antioxidant: alpha-tocopherol (or E 307).

Route of administration: Oral route

Version 1.0/Date: November 27th, 2023

Single dose: 0.5 ml (700 FCC ALU).

Maximum daily dose: 6 ml (8400 FCC ALU).

Lactacol/Lactazak® Characteristics

• Lactase is an enzyme derived from the fermentation of corn maltodextrin by Aspergillus oryzae

• Resistant to acidic gastric medium.

• Maintains its activity in the conditions of high pH variations.

17.2.1 Lactacol/Lactazak® Handling, Storage and Accountability Procedures:

The product will be provided by the Sponsor. Each patient will receive the necessary

amount of Lactacol/Lactazak®. The product must be stored at room temperature (25°), away from

heat sources, dry places and protected from light. The investigator will keep the

Lactacol/Lactazak® accountability during the entire duration of the study.

17.3 Criteria for discontinuation or removal of subjects from the study:

The Investigator may withdraw a subject from the study for any of the following reasons:

i. The subject suffers from significant inter-current illness or undergoes surgery during

the course of the study.

ii. The subject experiences an adverse event, and withdrawal would be in the best interest

of the subject.

Details of reasons for withdrawal of subjects will be recorded and reported.

The Investigator based on the subject's medical history and health status at the moment

of withdrawal/drop-out, in order to ensure the welfare of the subject, will decide the extent of the

follow-up safety procedures.

Pharm UNION

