26.1 Classification method for adverse events and serious adverse events

An **adverse event/experience** (AE) is any unwarranted medical occurrence in a patient. For the purposes of this document, this is intended to include any adverse event whether device related or not.

Adverse Event: Any untoward medical occurrence, unintended disease or injury or any untoward clinical signs (including an abnormal laboratory finding) in subjects, users, or other persons whether or not related to the investigational medic al device.

- NOTE 1: This includes events related to the investigational device or the comparator.
- NOTE 2: This includes events related to the procedures involved (any procedure in the clinical investigation plan).
- NOTE 3: For users or other persons this is restricted to events related to the investigational medical device.

Serious adverse event: adverse event that:

- a) led to death,
- b) led to serious deterioration in the health of the subject, that either resulted in:
 - 1) a life-threatening illness or injury, or
 - 2) a permanent impairment of a body structure or a body function, or
 - 3) in-patient or prolonged hospitalization, or
 - 4) medical or surgical intervention to prevent life-threatening illness or injury or permanent impairment to a body structure or a body function,
- c) led to foetal distress, foetal death or a congenital abnormality or birth defect.

Version 1.0/Date: November 27th, 2023

NOTE: Planned hospitalization for a pre-existing condition, or a procedure required by the CIP (Clinical Investigation Plan), without serious deterioration in health, is not considered a serious adverse event.

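### Section 17.3 does not separate stopping the product from leaving the study, so an infant withdrawn before Visit 2 has no scheduled post-baseline crying or bloating value

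*Protocol*

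**What the plan says.** The heading of protocol section 17.3 covers both discontinuation and removal, but the text gives a single action: "The Investigator may withdraw a subject from the study for any of the following reasons". Two reasons follow. The first is significant intercurrent illness or surgery. The second is "The subject experiences an adverse event, and withdrawal would be in the best interest" of the subject. Reasons for withdrawal are recorded and reported. As to what happens next, the investigator, in view of the infant's health at the time "of withdrawal/drop-out, in order to ensure the welfare of the subject, will decide the extent of the" safety follow-up. Section 26 adds that adverse events are followed until they subside. No early-termination assessment of crying or bloating is given.

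Section 15 states: "Subjects will attend 3 visits during the study". Crying is evaluated at Visit 1, Visit 2 (Day 14 in the visit list, Day 15 ± 2 in the flowchart) and the Day 28 phone call. Bloating is evaluated at Visits 1 and 2. It also appears in the Day 28 visit list, but is not marked for that visit in the flowchart. The flowchart row "End of product administration" is marked at Visit 2.

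Section 16 makes crying episodes per day and bloating on a 3-point scale the primary endpoint. It names a daily journal only for child sleep, caregiver sleep and night awakenings, for example: "Change in mean number of hours of child sleep during 24 h, evaluated in a daily manner during study period through a journal". One safety endpoint is "Number of participants withdrawn due to lack of tolerability".

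**The concern.** Stopping a product and leaving a study are different events. The first is a treatment decision, after which the infant can still be observed. The second ends observation. Section 17.3 names only the second, so an investigator who follows it literally when an infant should stop the product will withdraw that infant and owe nothing further except safety follow-up.

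This study is exposed to that loss for three reasons. It has no comparator, so selective loss cannot partly cancel between arms. Its result is a before-after change, which cannot be formed without a later value. It enrols only 30 infants. If the infants withdrawn are those who tolerate the product badly or whose symptoms worsen, the reported change in crying describes mainly those who stayed. Post-withdrawal data collection is a matter of conduct that has to be fixed before enrolment. An analysis plan can impute, but it cannot recover evaluations that were never made.

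**Working it through.** **1. What remains after withdrawal** (visit list and flowchart, section 15)

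| Time of withdrawal | Scheduled post-baseline crying values left | Scheduled post-baseline bloating values left |
|---|---|---|
| Before Visit 2 | 0 of 2 | 0 of 1 (flowchart) or 0 of 2 (visit list) |
| Between Visit 2 and Day 28 | 1 of 2 | 1 of 1 or 1 of 2 |

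The window before Visit 2 spans essentially the whole 14-day product period. The journal does not fill the gap, since section 16 names it only for sleep and awakenings. Section 15 also says that assessments are made periodically under routine practice, so an unscheduled value might exist. The table counts scheduled values only.

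**2. Could the reason for withdrawal be linked to the outcome?**

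- For a link: section 26.1 defines an adverse event as "Any untoward medical occurrence, unintended disease or injury or any untoward clinical signs". Section 26.2 has discrete episodes of chronic conditions reported as adverse events, in order to assess changes in their frequency or severity. The section 16 endpoint on tolerability withdrawals shows that such withdrawals are foreseen.
- Against a link: section 26.2 puts symptoms present before the study in the medical history. Lack of effect is not a listed withdrawal reason in section 17.3. Intercurrent illness or surgery need not relate to colic.

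A link is possible, but the text does not settle it for colic.

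**3. Size**

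The protocol has no figure to reproduce: N = 30 is given without an effect size, SD or dropout rate. The number lost, k, is therefore an assumption.

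Share of primary data lost before Visit 2 = k/30:

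- k = 1: 1/30 = 3.3%
- k = 2: 2/30 = 6.7%
- k = 3: 3/30 = 10.0%

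Inflation of the mean change in crying: let D be the mean change among the 30 − k infants observed and cD the mean change the lost infants would have shown. The mean over all 30 is D(30 − k + kc)/30, so the observed mean exceeds it by the factor 30/(30 − k + kc).

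| Assumed c | k = 1 | k = 2 | k = 3 |
|---|---|---|---|
| 1 (same improvement) | 30/30 = 1.00 | 30/30 = 1.00 | 30/30 = 1.00 |
| 0.5 (half) | 30/29.5 = 1.02 | 30/29 = 1.03 | 30/28.5 = 1.05 |
| 0 (none) | 30/29 = 1.03 | 30/28 = 1.07 | 30/27 = 1.11 |
| −0.5 (worse by half as much) | 30/28.5 = 1.05 | 30/27 = 1.11 | 30/25.5 = 1.18 |

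The last row matters because worsening is the mechanism that would make the loss informative; stopping at c = 0 would understate that case. In the other direction, section 8 says that colic resolves by 12 weeks of age in 60% of infants, so some lost infants would probably have improved anyway.

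For bloating, if the result were a proportion improved out of 30, k missing infants leave a best-to-worst-case range of k/30, that is 3.3, 6.7 or 10.0 percentage points. Section 29 uses N as the denominator for percentages. If N means all enrolled infants, missing ones lower the proportion improved, so the lean toward infants who stay applies mainly to the mean change in crying.

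**The case against.** The strongest reply is that silence is being read as restriction. Section 17.3 says that the investigator may withdraw an infant. It does not say that an infant who stops the product must leave. Section 15 does not make visit attendance depend on product use, and the flowchart lists product administration separately from the evaluations. In a study of a food supplement in routine practice, a clinician can stop the product without a clause permitting it. This stands. A reader might infer that the protocol forces out every infant with an adverse event, or forbids stopping and staying; it does neither. An infant who is not withdrawn remains due for all three visits. What survives is narrower: the protocol names no such route, so handling is left to each investigator, and those who use the clause as written lose primary data.

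Second, bias needs a chain of events: colic worsens, the worsening is recorded as an adverse event, the investigator chooses withdrawal from the study, and this happens before Visit 2. This also stands. It would be wrong to conclude that the crying result will be biased.

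Third, late off-product values mix in natural recovery, and how they enter the main result may be settled in an analysis plan that is not shown. That is a reason to flag such values, not to leave them uncollected.

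Fourth, it is tempting to say that Day 28 already observes every infant off product. The 14-day course implies this but does not assure it: sections 8 and 17.1 describe use through the first 3 to 4 months with gradual withdrawal. The fix does not depend on it, since a Day 28 phone evaluation is scheduled either way.

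**Conclusion.** The point holds in a limited form. As written, section 17.3 treats stopping for an adverse event or intercurrent illness as discretionary withdrawal from the study followed by safety follow-up alone. An infant withdrawn before Visit 2 then contributes no scheduled post-baseline value to either primary outcome.

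The loss of data is certain for each such infant. The bias is conditional on the withdrawal being related to symptoms or tolerability. Its size is unknown and probably modest. The factors in the table, from 1.00 up to 1.11 for lost infants who do not improve and higher if they worsen, rest on an assumed 1 to 3 losses, all before Visit 2. They should not be read as an estimate of what will happen. This is a worthwhile, inexpensive improvement to the conduct rules, and not a flaw that invalidates the study.

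**What to change.** In section 17.3, state that the product may be stopped, with date and reason recorded, without ending participation. With caregiver consent, such infants complete the Visit 2 and Day 28 evaluations of crying, bloating and sleep, by phone if needed. Values obtained after stopping are flagged as off-product, so that spontaneous improvement is not credited to the product and can be shown separately. Withdrawal from the study remains available, and neither the clinical threshold for stopping nor the caregiver's right to leave changes.

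In section 16, keep the count of withdrawals for lack of tolerability, and add a separately reported count of infants whose product was stopped for intolerance but who stayed in the study. Without this, the new option would remove them from the tolerability endpoint.

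The cost is a few sentences in two sections, possibly one CRF field (the CRF is not shown) and a few phone assessments. The efficacy and tolerability figures may come out slightly less favourable.
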